## 6.6.2 Emergency breaking of assigned treatment code

Emergency code breaks must only be undertaken when it is required to in order to treat the patient safely. Most often, study treatment discontinuation and knowledge of the possible treatment assignments are sufficient to treat a study patient who presents with an emergency condition. Emergency treatment code breaks are performed using the IRT. When the investigator contacts the system to break a treatment code for a patient, he/she must provide the requested patient identifying information and confirm the necessity to break the treatment code for the patient. The investigator will then receive details of the investigational drug treatment for the specified patient and a fax or email confirming this information. The system will

automatically inform the Novartis monitor for the site and the study team that the code has been broken.

It is the investigator's responsibility to ensure that there is a dependable procedure in place to allow access to the IRT/code break cards at any time in case of emergency. The investigator will provide:

- Protocol number
- Name (if available)
- Patient number

In addition, oral and written information to the patient must be provided on how to contact his/her backup in cases of emergency, or when he/she is unavailable, to ensure that un-blinding can be performed at any time.

### 6.7 Preparation and dispensation

Each study site will be supplied with study drug in packaging as described under investigational and control drugs section (Section 6.1.1).

A unique medication number is printed on the study medication label.

For the double-blind period, investigator staff will select the study treatment to dispense to the patient as per the treatment assigned to the patient by contacting the IRT and obtaining the medication numbers.

For the open-label period, investigator staff will identify the study medication kits to dispense to the patient by contacting the IRT and obtaining the medication numbers.

The study medication has a 2-part label (base label plus tear-off label). Immediately before dispensing the medication kit to the patient, site personnel will detach the outer part of the label (tear-off label) from the packaging and affix it to the source document.

In the event of a major healthcare disruption (e.g., a pandemic or epidemic) that limits or prevents on-site visits to the study site, study drug may be shipped or provided directly to patients for home administration if needed. When site visits are not possible, regular phone calls/virtual contacts or visits of site staff to the patient's home, depending on local regulations and capabilities (according to visit schedule or more frequently if needed, and weekly when patient is receiving weekly dosing) will occur between the site and the patient for instructional purposes, for safety monitoring and review of the patient's ophthalmological and general health status until the patient can again visit the site. This is necessary to ensure that there are no safety concerns to the patient requiring treatment interruption or discontinuation. If in the opinion of the investigator the patient requires an in-person assessment, arrangements will be made for the patient to be evaluated at the site, or if this is not feasible, by a local ophthalmologist or in an emergency healthcare setting. In consultation with the investigator, selected ophthalmological assessments (e.g., visual acuity, intraocular pressure, color vision) can also be done by a local optometrist to enable continuous monitoring of the patient's ophthalmological status if on-site visits or visits to a local ophthalmologist are not feasible. Assessment results must be reported to and discussed with the investigator as soon as possible in this case.

Novartis	Confidential	Page 51 of 99
Amended Protocol (Version No. 0	)2 Track Changes)	Protocol No. CAIN457ADE16

Delivery of the Investigational Medicinal Product (IMP) directly to a patient's home is at the discretion of the investigator and would be permitted only during the duration of the healthcare disruption. The patients will be supplied with material to document the home administration and to allow accountability of the study medication. At the site level, the agreement with/approval of the investigator should be obtained to implement home delivery.

### 6.7.1 Handling of study treatment and additional treatment

### 6.7.1.1 Handling of study treatment

Study treatment must be received by a designated person at the study site, handled and stored safely and properly and kept in a secure location to which only the investigator and designated site personnel have access. Upon receipt, all study treatment must be stored according to the instructions specified in the IB.

Clinical supplies are to be dispensed only in accordance with the protocol. Technical complaints are to be reported to the respective Novartis Country Organization (CO) Quality Assurance.

Medication labels will be in the local language and comply with the legal requirements of each country. They will include storage conditions for the study treatment but no information about the patient except for the medication number.

The investigator must maintain an accurate record of the shipment and dispensing of study treatment in a drug accountability log. Monitoring of drug accountability will be performed by monitors during site visits or remotely and at the completion of the trial. Patients will be asked to return all unused study treatment and packaging at the end of the study or at the time of discontinuation of study treatment (in case home administration became necessary, i.e., in case of a major healthcare disruption).

At the conclusion of the study, and as appropriate during the course of the study, the investigator will return all unused study treatment, packaging, drug labels, and a copy of the completed drug accountability log to the Novartis monitor or to the Novartis address provided in the investigator folder at each site.

### 6.7.1.2 Handling of additional treatment

### 6.7.2 Instruction for prescribing and taking study treatment

Secukinumab solution for s.c. injection or placebo solution will be provided in PFS as described in Section 6.1.1.

Each patient will require 1 box (containing  $2 \times PFS$ ) for each treatment visit throughout the study, i.e.,

- Two secukinumab 150 mg PFS **OR** two secukinumab placebo 150 mg PFS during the double-blind period.
- Two secukinumab 150 mg PFS during the open-label period.

Patients will be assigned to treatment as described in Section 6.1.3.

All study treatment kits assigned by the IRT will be recorded in the IRT system.

### Administration

Administration of all doses of study treatment at the study site should be performed after the study assessments for the specific visit, including blood sampling and QoL questionnaire, have been completed.

The first study treatment administration will occur at the Baseline Visit, after all study scheduled assessments for this visit have been performed (and inclusion/exclusion criteria confirmed) and only after the scheduled blood samples have been drawn.

Prior to administration, the boxes containing the PFS with study treatment solution should be allowed to come to room temperature unopened. Used PFS should be disposed immediately after use in a sharps container **OR** according to local regulations.

The study treatment solution must be injected s.c. in intact areas of the skin. If possible throughout the trial, the study treatment should be administered to one of the following body regions, rotating the injection site from visit to visit: right thigh, left thigh, right stomach, left stomach, upper outer arm (when assisted by site personnel).

All dates and times of injections during the study must be recorded on the appropriate CRF.

In the event of a major healthcare disruption (e.g., a pandemic or epidemic) that limits or prevents on-site visits to the study site, home administration of the study drug is permitted as described above (Section 6.7). Home administration can be performed by the patient, a trained caregiver, or study personnel. Study participants or caregivers will be trained adequately on how to perform administration of the study treatment, if not already trained. If the patient or caregiver is not trained for drug administration and cannot visit the site to undergo training, the site can consider providing suitable virtual training and oversight. A joint decision together with the patient or caregiver should be made as to whether this constitutes sufficient training and oversight.

# 7 Informed consent procedures

Eligible patients may only be included in the study after providing IRB/IEC-approved informed consent.

Informed consent must be obtained before conducting any study-specific procedures (e.g., all of the procedures described in the protocol). The process of obtaining informed consent must be documented in the patient source documents.

Information about common side effects already known about the investigational drug can be found in the IB. This information will be included in the patient informed consent and should be discussed with the patient during the study as needed. Any new information regarding the safety profile of the investigational drug that is identified between IB updates will be communicated as appropriate, for example, via an investigator notification (IN) or an aggregate safety finding. New information might require an update to the informed consent and then must be discussed with the patient.

Novartis	Confidential	Page 53 of 99
Amended Protocol (Version No.	02 Track Changes)	Protocol No. CAIN457ADE16

Women of child-bearing potential must be informed that taking the study treatment may involve unknown risks to the fetus if pregnancy were to occur during the study and agree that in order to participate in the study they must adhere to the contraception requirements.

### 8 Visit schedule and assessments

The Assessment Schedule (Table 8-1 and Table 8-2) lists all of the assessments and when they are performed. All data obtained from these assessments must be supported in the patient's source documentation.

Patients should be seen for all visits/assessments as outlined in the assessment schedule (Table 8-1 and Table 8-2) or as close to the designated day/time as possible. Missed or rescheduled visits should not lead to automatic discontinuation.

Participants who prematurely discontinue the study for any reason should be scheduled for a visit as soon as possible, at which time all of the assessments listed for the study discontinuation visit will be performed. This study discontinuation visit should include all assessments of the Week 16 (if discontinued during double-blind treatment), NR32 (for non-responders), R16 (for relapsers) or Week 68 (for patients who discontinued during the follow-up period) visit. See also Section 9.1.1.

At this study discontinuation visit, dispensed investigational product should be reconciled, and the AEs and concomitant medications recorded on the CRF.

In the event of a major healthcare disruption (e.g., a pandemic or epidemic) that limits or prevents on-site visits to the study site, regular phone calls/virtual contacts or visits of site staff to the patient's home, depending on local regulations and capabilities, will occur (according to the visit schedule or weekly if during the weekly dosing period) for instructional purposes, for safety monitoring and review of the patient's ophthalmological and general health status until the patient can again visit the site. This is necessary to ensure that there are no safety concerns to the patient requiring treatment interruption or discontinuation. If in the opinion of the investigator the patient requires an in-person assessment, arrangements will be made for the patient to be evaluated at the site, or if this is not feasible, by a local ophthalmological assessments (e.g., visual acuity, intraocular pressure, color vision) can also be done by a local optometrist to enable continuous monitoring of the patient's ophthalmological status if on-site visits or visits to a local ophthalmologist are not feasible. Assessment results have to be reported to and discussed with the investigator as soon as possible in this case.

Events qualifying for being reported in the case report form (e.g., AEs, etc.) should be entered as appropriate.

Special efforts should be made to conduct the Week 16, R16 and NR16 visits on-site, if feasible. If it is not feasible to conduct these visits on-site, visits to the patient's home or a virtual visit if a home visit not feasible, should be attempted. Patients should be reminded to be fasting prior to visits with laboratory assessments.

Period	Screening Period	Treatment Period							Post-Treatment Follow-Up 							
Visit Name	Screening (Week -6 to Baseline)	Baseline	Week 1	Week 2	Week 3	Week 4	Week 8	Week 12	Week 16	Week 20	Week 24	Week 32	Week 40	Week 56	Week 68	USV 
Days	-42 to -1	1	8	15	22	29	57	85	113	141	169	225	281	393	477	
Informed consent	Х															
Demography	Х															
Inclusion/exclusion criteria	Х	Х														
Washout evaluation/instruction	S	S														
Relevant medical history	Х	(X)														
Smoking history/status	Х	Х														
TED medical history	Х	(X)														
Physical examination	S	S					S		S		S		S		S	(S)
Ophthalmologic assessment 	Х	Х		Х		Х	Х	Х	Х	Х	Х	Х	Х	Х	Х	(X)
Height	Х															
Weight	Х	Х							Х							
Vital signs	Х	Х	Х	Х	Х	Х	Х	Х	Х	Х	Х	х	Х	Х	Х	(X)
12-Lead ECG	S															
Hematology and blood chemistry (fasting)	Х	Х				Х	х	х	х	Х	Х					(X)
Urinalysis (local analysis) 	S	S							S		S					(S)

### Table 8-1 Assessment schedule (double-blind treatment period and follow-up for responders at Week 16)

### Novartis Amended Protocol (Version No. 02Track Changes)

### Page 55 of 99 Protocol No. CAIN457ADE16

Period	Screening Period		Treatment Period Post-Treatment Follow-Up 													
Visit Name	Screening (Week -6 to Baseline)	Baseline	Week 1	Week 2	Week 3	Week 4	Week 8	Week 12	Week 16	Week 20	Week 24	Week 32	Week 40	Week 56	Week 68	USV 
Days	-42 to -1	1	8	15	22	29	57	85	113	141	169	225	281	393	477	
Thyroid laboratory test (fasting)	х	х				х	х	х	х	х	х	х	х	х	х	(X)
QuantiFERON TB-PLUS test	x															
Serum pregnancy test	Х															
Urine pregnancy test (local analysis)		S				s	s	S	S	S	S	S	S		S	(S)
Adverse events (including injections site reactions)	Х	Х	Х	Х	Х	Х	Х	х	Х	Х	х	Х	Х	Х	х	Х
						i	i				i.					
Responder/NR-assessment									Х							
Prior/concomitant medications/non-drug therapy							Updat	te as neo	cessary							
CAS	Х	Х		Х		х	Х	Х	х	х	Х	Х	Х	х	Х	(X)
Proptosis measurement	Х	Х		Х		Х	Х	Х	Х	Х	Х	Х	Х	Х	Х	(X)
Diplopia grading 	Х	Х		Х		Х	Х	Х	Х	Х	Х	Х	Х	Х	Х	(X)
GO-QoL		Х		Х		Х	Х	Х	Х	Х	Х	х	х	Х	х	
Contact Interactive Response Technology (IRT)	x	Х	Х	Х	х	Х	х	х	х							

Confidential

Novartis	
Amended Protocol (Version No. 02Track Changes)	

#### Page 56 of 99 Protocol No. CAIN457ADE16

Period	Screening Period	Treatment Period								Post-Treatment Follow-Up 						
Visit Name	Screening (Week -6 to Baseline)	Baseline	Week 1	Week 2	Week 3	Week 4	Week 8	Week 12	Week 16	Week 20	Week 24	Week 32	Week 40	Week 56	Week 68	USV 
Days	-42 to -1	1	8	15	22	29	57	85	113	141	169	225	281	393	477	
Randomization		Х														
Study drug administration		Х	Х	Х	Х	Х	Х	Х								

Confidential

X = assessment to be recorded in the clinical database or received electronically from a vendor.

S = source data.

1 = Ophthalmic examination (please refer to Section 8.3.4).

2 = For responders only. Non-responders and patients who relapse during follow-up, will receive a second treatment course (see next table).

3 = Unscheduled visits (USV) might be required e.g., if patients observe symptoms between scheduled visits or for safety reasons. The safety assessments listed herein may be performed at the discretion of the investigator as needed to resolve the reason for the unscheduled visit. (S)AE assessment and concomitant medications are mandatory for all unscheduled visits.

4 = Kits for urinalysis will be provided by central lab and test is performed locally.

6 = Gorman score/subjective diplopia score (Bahn et al 1987).

() = Parentheses denote assessments that are on a per need basis at investigator's discretion.

### Table 8-2 Assessment schedule (re-treatment for non-responders and relapsers)

Period	Second C	ourse Trea	tment Perio	d					Post-Trea	w-Up	
Visit name non-responder	Week NR16 	Week NR17	Week NR18	Week NR19	Week NR20	Week NR24	Week NR28	Week NR32	Week NR40	Week NR56	USV 
Days	113	120	127	134	141	169	197	225	281	393	
Visit name relapsers§	Week R0 	Week R1	Week R2	Week R3	Week R4	Week R8	Week R12	Week R16	Week R24	Week R40	USV 
Days since relapse	1	8	15	22	29	57	85	113	169	281	
Physical examination	S					S		S	S		(S)
Ophthalmologic assessment 	Х		Х		х	Х	х	х	Х	х	(X)
Weight	Х							Х			
Vital signs	Х	Х	Х	х	Х	Х	Х	х	Х	х	(X)
Hematology and blood chemistry (fasting)	Х				х	Х	х	х	х		(X)
Urinalysis (local analysis) 	S							S	S		(S)
Thyroid laboratory assessments (fasting)	Х				Х	Х	Х	Х	Х	Х	(X)
Urine pregnancy test (local analysis)	S				S	S	S	S	S	S	(S)
Adverse events (including injections site reactions)	Х	Х	Х	Х	Х	Х	Х	Х	x	Х	Х
Responder/NR-assessment								Х			
Prior/concomitant medications/non-drug therapy			1	1	Upd	ate as neces	ssary	1		1	
	V		V		V	V	v	V	v	v	(X)
CAS	Х		Х		Х	Х	Х	Х	Х	Х	(X)

#### Novartis Amended Protocol (Version No. 02Track Changes)

#### Page 58 of 99 Protocol No. CAIN457ADE16

Period	Second C	Second Course Treatment Period				Post-Treatment Follow-Up					
Visit name non-responder	Week NR16 	Week NR17	Week NR18	Week NR19	Week NR20	Week NR24	Week NR28	Week NR32	Week NR40	Week NR56	USV 
Days	113	120	127	134	141	169	197	225	281	393	
Visit name relapsers§	Week R0 	Week R1	Week R2	Week R3	Week R4	Week R8	Week R12	Week R16	Week R24	Week R40	USV 
Days since relapse	1	8	15	22	29	57	85	113	169	281	
Proptosis measurement	Х		Х		Х	Х	Х	Х	Х	Х	(X)
Diplopia grading 	Х		Х		Х	Х	х	Х	х	Х	(X)
GO-QoL	Х		Х		х	х	х	Х	Х	х	
Contact Interactive Response Technology (IRT)	х	Х	Х	х	х	х	х	х			
Study drug administration*	Х	Х	Х	Х	Х	Х	Х				

Confidential

\* = Patients who are non-responders at Week 16 or patients who relapse during follow-up receive 16 weeks of treatment with open-label secukinumab.

§ = Relapse can occur at any time during the 52-week follow-up period (i.e., from Week 16 onward to Week 68).

X = assessment to be recorded in the clinical database or received electronically from a vendor. S = source data.

1 = Ophthalmic examination (please refer to Section 8.3.4).

2 = Unscheduled visits (USV) might be required e.g., if patients observe symptoms between scheduled visits or for safety reasons. The safety assessments listed herein may be performed at the discretion of the investigator as needed to resolve the reason for the unscheduled visit. (S)AE assessment and concomitant medications are mandatory for all unscheduled visits.

3 = Kits for urinalysis will be provided by central lab and test is performed locally.

4 = Only applicable for assessments that have not been performed at the W16 Visit in non-responders.

5 = Only applicable for assessments that have not been performed at the Visit at which relapse was diagnosed.

6 = Gorman score/subjective diplopia score (Bahn et al 1987).

() = Parentheses denote assessments that are on a per need basis at investigator's discretion.

# 8.1 Screening

Patient's eligibility for the study will be assessed during the Screening period (Day -42 to -1) and at the Baseline Visit (see Table 8-1).

Patients who fail Screening for any reason may be re-screened once. Patients who are re-screened must sign a new ICF and be issued a new Patient No. before any study-related assessment is performed or any data for the Screening Period are collected for the patient under the new Patient No.

The Investigator or qualified site staff will record all re-screenings on the Re-screening eCRF page and any applicable Screening numbers the patient was issued prior to the current Screening number. The date of the new informed consent signature must be entered on the Informed Consent eCRF page to correspond with the new Screening Patient No.

The Withdrawal of Consent eCRF page must be completed if consent was withdrawn during the Screening Period before the patient was randomized.

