	
 
Clinical diagnosis of active, moderate to severe TED (not sight-threatening) in the study eye at Baseline associated with 2 or more of the following:         
 
Lid retraction ≥ 2 mm
 
Moderate or severe soft tissue involvement
 
Exophthalmos ≥ 3 mm above normal
 
Inconstant or constant diplopia
 
 
 

	Onset of TED symptoms fewer than 12 months prior to Baseline.
	
 
CAS ≥ 4 (on a 7-point scale, with a score of ≥ 3 indicating active TED) in the more severely affected (study) eye at Screening and Baseline. Note: Proptosis is the primary qualifier for selection of the study eye. In case both eyes show a similar degree of proptosis, other inflammatory signs and symptoms (CAS) should be taken into account by the investigator for the selection of the study eye.
 

	
 
Peripheral euthyroidism or mild hypo-/hyperthyroidism defined as free T3 (fT3) and free T4 (fT4) < 30% above/below normal limits at Screening. Every effort should be made to correct the mild hypo- /hyperthyroidism promptly and to maintain the euthyroid state until the end of this study.
 
Note: Central lab retests will be allowed during the Screening Period if fT3 and fT4 values are outside the above-mentioned cut-off criteria.
 

	• Orbital MRI assessment available confirming the diagnosis of TED for patients initially presenting with hypo- or euthyroidism (without treatment for hyperthyroidism) before or at the time of TED diagnosis (to rule out other potential causes of orbital signs and symptoms.
Key exclusion criteria	
 
Improvement in CAS of ≥ 2 points and/or improvement in proptosis of ≥ 2 mm in the study eye between Screening and Baseline.
 

	• Signs of sight-threatening TED defined by optic neuropathy or severe corneal injury.
	• Patients, in the opinion of the investigator, requiring immediate or urgent medical treatment with glucocorticoids for TED.
	• Patients requiring immediate surgical ophthalmological intervention or planning corrective surgery/irradiation during the course of the study.
	• Decreased best corrected visual acuity (BCVA) as defined by a decrease in vision of 2 lines on the Snellen chart, new visual field defect or color defect within the last 6 months.
	• Any other ophthalmic and/or orbital disease or condition that might interfere with the assessment of TED.
	Previous orbital radiotherapy.

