### Screening period (Week -6 to Baseline)

Patients' eligibility will be assessed during the Screening Period, which will occur for a maximum of 6 weeks. In the event of a major healthcare disruption (e.g., a pandemic, or epidemic) that limits or prevents on-site visits to the study sites the Screening Period may be extended to a maximum of 8 weeks before Baseline.

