# 5.2 Exclusion criteria

Patients meeting any of the following criteria are not eligible for inclusion in this study:

- 1. Improvement in CAS of  $\geq 2$  points and/or improvement in proptosis of  $\geq 2$  mm in the study eye between Screening and Baseline.
- 2. Signs of sight-threatening TED defined by optic neuropathy or severe corneal injury.
- 3. Patients, in the opinion of the investigator, requiring immediate or urgent medical treatment with glucocorticoids for TED.
- 4. Patients requiring immediate surgical ophthalmological intervention or planning corrective surgery/irradiation during the course of the study.
- 5. Decreased best corrected visual acuity (BCVA) as defined by a decrease in vision of 2 lines on the Snellen chart, new visual field defect or color defect within the last 6 months.
- 6. Any other ophthalmic and/or orbital disease or other condition that might interfere with the assessment of TED.
- 7. Previous orbital radiotherapy.
- 8. Previous ophthalmological/orbital surgery for TED (e.g., orbital decompression).
- 9. Previous use of biological agents for the treatment of TED.
- 10. Previous use of systemic, non-biological, immunomodulatory agents for the treatment of TED (e.g., mycophenolate or cyclosporine).
- 11. Previous exposure to secukinumab or other biologic drugs directly targeting IL-17A or the IL-17 receptor (e.g., ixekizumab, brodalumab).
- 12. Previous treatment with rituximab, tocilizumab or teprotumumab.
- 13. Previous use of systemic corticosteroids for the treatment of TED, except for oral corticosteroids with a cumulative dose equivalent to < 1 g oral prednisone/prednisolone if the corticosteroid was discontinued at least 4 weeks prior to Baseline.
- Previous treatment with any cell-depleting therapies including but not limited to anti-CD20 or investigational agents (e.g., CAMPATH, anti-CD4, anti-CD5, anti-CD3, anti-CD19).
- 15. Use of other investigational drugs within 5 half-lives of enrollment or within 30 days, whichever is longer.
- 16. Previous or ongoing use of prohibited treatments (see Section 6.2.2). Respective washout periods detailed in this section must be adhered to.
- 17. History of hypersensitivity to any of the study drug constituents.
- 18. Pregnant or nursing (lactating) women.

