### 8.1.1 Information to be collected on screening failures

Patients who sign an ICF and subsequently found to be ineligible prior to randomization will be considered a Screen Failure. All reasons for a Screen Failure should be recorded on the appropriate CRF. The demographic information, informed consent, and Inclusion/Exclusion pages must also be completed for Screen Failure patients. No other data will be entered into the clinical database for patients who are Screen Failures, unless the patient experienced a SAE during the Screening Phase (see Section 10.1.3 for SAE reporting details). If the patient fails to be randomized, the IRT must be notified within 2 days of the Screen Fail that the patient was not randomized.

Patients who are randomized and fail to start treatment will be considered an early terminator. The reason for early termination should be recorded on the appropriate CRF.

Patients randomized in error (= mis-randomized subjects) are defined as those subjects who were mistakenly randomized into the IRT prior to the site confirming all eligibility criteria had been met and to whom no study medication was given. Mis-randomized subjects will be treated as Screen Failures.

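### Section 8.1 lets some patients excluded for improvement before Baseline be re-screened with their improved values as the new reference

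*Protocol*

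**What the plan says.** Exclusion criterion 1 (Protocol Section 5.2, and in the same terms in the Protocol summary) is "Improvement in CAS of ≥ 2 points and/or improvement in proptosis of ≥ 2 mm in the study eye between Screening and Baseline".

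Under Section 8.1.1 a consented patient "subsequently found to be ineligible prior to randomization will be considered a Screen Failure". This covers a patient found at the Baseline visit to have improved too much.

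Section 8.1 then allows a second attempt: "Patients who fail Screening for any reason may be re-screened once". That attempt is a fresh start: "Patients who are re-screened must sign a new ICF and be issued a new Patient No. before any study-related assessment is performed". Screening data are collected anew under the new number.

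Section 3 gives the Screening period an upper limit, "which will occur for a maximum of 6 weeks" (8 weeks during a major healthcare disruption), but no lower one. For the failed first attempt, Section 8.1.1 keeps the reason for failure and the demographic, consent and eligibility pages. Beyond these, apart from a serious adverse event, "No other data will be entered into the clinical database for patients who are Screen Failures". The first CAS and proptosis values are therefore not in the database.

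Section 5.2 closes by telling investigators not to add exclusions of their own. Unless one of the listed judgement-based criteria applies, a site has no basis in the text for refusing a patient who qualifies on the new values.

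**The concern.** Exclusion 1 uses the same study-eye thresholds, 2 points and 2 mm, as the primary response in Plan A (overall response) and Plan B (proptosis response). Its evident effect is to keep out patients who are already improving untreated by an amount that the trial would call a response. The protocol does not state that aim; it is inferred from the thresholds.

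The re-screening rule makes no distinction by reason for failure. The patients whom exclusion 1 removes may come back, and the change that removed them is no longer visible to the criterion. If such patients tend to go on improving without treatment, some would be counted as responders on placebo. That would raise the placebo rate, narrow the difference and cost power.

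**Working it through.** **1. Does the route exist?** An exclusion 1 failure is a screen failure (8.1.1). Any screen failure may be re-screened once (8.1). Screening data start again (8.1). Exclusion 1 compares only the values "in the study eye between Screening and Baseline" and does not say which Screening. No section bars re-screening after this failure, sets a minimum interval before it, or keeps the first value as reference. The route exists.

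**2. How wide is it on the CAS limb?** Inputs: CAS runs from 0 to 7 (Section 8.3.1); inclusion 5 requires CAS of at least 4 at Screening and at Baseline; exclusion 1 is triggered by a fall of at least 2. Re-entry at the improved score needs (first Screening CAS − 2) ≥ first Baseline CAS ≥ 4, so the first Screening CAS must be 6 or 7.

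| First Screening CAS | First Baseline CAS that triggers exclusion 1 | Of these, still ≥ 4 |
|---|---|---|
| 4 | 0–2 | none |
| 5 | 0–3 | none |
| 6 | 0–4 | 4 |
| 7 | 0–5 | 4, 5 |

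Example: CAS 6 then 4 is excluded; after new consent, 4 then 4 passes both inclusion 5 and exclusion 1.

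**3. How wide on the proptosis limb?** There is no minimum proptosis for entry. Exophthalmos is one of four features in inclusion 3, of which two are needed. Any fall of 2 mm or more can therefore be followed by re-entry if CAS is still at least 4, two features remain, symptom onset is still under 12 months before the new Baseline, and all other criteria hold. Example: 24 mm then 22 mm is excluded; 22 mm then 22 mm on re-screening passes exclusion 1.

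**4. The plan's own power figures.** Inputs from Section 12.8.1: 60% against 20%, 35 per arm, 5% level (two-sided, Section 12.4.2), continuity-corrected chi-squared test. With d = p1 − p0, the effective size after the correction is n′ = n − 2/d + 1/(n d²), and

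power = Φ{[d√n′ − 1.96 √(2 p̄ q̄)] / √(p1 q1 + p0 q0)}, where p̄ = (p1 + p0)/2 and each q = 1 − p.

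For p0 = 0.20: n′ = 35 − 5 + 0.18 = 30.18 and power = 0.908. The required size comes to 35 per arm, as stated.

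| Placebo rate | Protocol | Recomputed |
|---|---|---|
| 0.175 | 0.94 | 0.946 |
| 0.20 | 0.90 | 0.908 |
| 0.225 | 0.85 | 0.856 |

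The plan's figures reproduce.

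**5. What re-admission could do to power.** Assume that a share f of patients are re-screened improvers, that they respond on placebo with probability r, and that the secukinumab rate stays at 60%. Then p0 = (1 − f) × 0.20 + f × r. Neither f nor r is in the documents; the values below are illustrations.

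| f | r | p0 | Power |
|---|---|---|---|
| any | 20% | 0.20 | 0.91 |
| 5% | 40% | 0.21 | 0.89 |
| 10% | 40% | 0.22 | 0.87 |
| 10% | 60% | 0.24 | 0.82 |
| 20% | 40% | 0.24 | 0.82 |
| 20% | 60% | 0.28 | 0.70 |

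The effect runs from nothing, if these patients respond on placebo like everyone else, to a material loss if they are common and respond often.

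**The case against.** The strongest reply is that the safeguards largely survive re-screening. Only one further attempt is allowed. Exclusion 1 applies again over the new window, so a patient who keeps improving by 2 points or 2 mm is excluded again. The CAS floor closes most of the CAS route. A patient who is stable over the second window has arguably shown what the criterion asks for, and part of the first change may have been noise: Section 9.1.1 itself recognises that ocular findings fluctuate within a patient. The lack of a minimum screening interval is not peculiar to re-screening either; it holds for first attempts too.

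Most of this stands and limits the point. It does not remove it. The second window starts from the improved value and may be shorter than the first, whereas response is judged over 16 weeks. It is also true that response is counted from the new Baseline, so the earlier fall never scores as response. But response is counted from Baseline for every patient, so this does not show that exclusion 1 still does its work.

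A reader might infer three stronger things, which the documents do not support:

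- *That the two rules cancel each other.* They do not, for the reasons in the first paragraph.
- *That the treatment comparison is biased.* Re-screened patients are randomised 1:1 like the rest, so the arms stay comparable; the risk is dilution.
- *That each re-admitted responder on placebo costs a full patient's worth of response rate, to be read against the protocol's power table.* That table concerns assumed true rates. The patient who would otherwise fill the place is already assumed to respond 20% of the time, so the expected excess per such placebo patient is (r − 0.20)/35, with r unknown. SAP Section 1.2 also reports no responders at premature discontinuation, so the documents show no sign of an inflated placebo rate in this trial.

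**Conclusion.** The concern holds in a limited form. Section 8.1 permits re-screening after an exclusion 1 failure and leaves the reference value undefined, so the criterion can be bypassed by patients who still meet everything else: three CAS patterns (6 to 4, 7 to 5, 7 to 4), and any qualifying proptosis fall if CAS stays at 4 or more and two of the four features remain.

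The consequence is a possible rise in placebo response and loss of power. Its size cannot be estimated, because the documents give neither the number of such patients nor their response rate. The conclusion that there is any loss rests on the assumption that these patients respond on placebo more often than the planned 20%.

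The planned sample size is unaffected. The SAP reports termination with 28 patients randomised and omits superiority testing, so no confirmatory result depends on this. It is a cheap improvement to the wording, chiefly of value if the protocol text is reused.

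**What to change.** Either of two changes would do.

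1. In Section 8.1, state: *One re-screen is permitted after screen failure, unless the patient failed exclusion criterion 1.* This is one sentence.
2. In Section 8.1, state that on re-screening exclusion 1 is assessed against the CAS and proptosis of the first Screening visit. Section 8.1.1 and the eCRF must then also change so that those two values are recorded for screen failures, which they currently are not.

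The first is simpler. The cost of either is a few patients lost to re-screening, including some whose first change was only fluctuation.
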